7.1. Outcomes and summary measures

The questionnaire asks patients to report on satisfaction with their cancer care using the CAHPS Cancer Care Survey. This outcome is classified as the Type 3 outcome in Table 12.

7.2. Data Analysis

Aim 2d survey methods and sampling mirrors Aim 2c (PROMIS items). Following Section 6.2 (Analysis of Outcomes classified as Type 3), we will perform the analysis for these continuous outcomes. We will use the AHRQ's CAHPS Analysis Program.^{21,22}

8. Analysis for Aim 3a: Patient adoption, clinician utilization, and their perspectives on appropriateness and acceptability

8.1. Outcomes and summary measures

The outcomes investigated in Aim 3a in the SIMPRO study are classified into four groups, depending on the data source and data collection schedule. **Table 13** shows the details of the groups and the disposition of each outcome in Aim 3a.

Table 13: Outcomes in Aim 3a

Type	Outcome Type in the SIMPRO study	Example outcomes in Aim 3a
1	Measured at one single time point only either in post-intervention (the intervention condition) or in pre-intervention (the control condition) for all or selected subjects (patients or providers)	Qualitative feedback Pt satisfaction with eSyM tool System Usability Items FIM item AIM items (acceptability) NOMAD items CSAT items # of med onc clinics continuing to use eSyM after stepped wedge period # of surg clinics continuing to use eSyM after stepped wedge period # of clinics that have >= 1 team conducting eSyM severe symptom outreach (e.g. using IB alerts) # of clinics that have >= 1 team conducting eSyM population symptom mgmt (e.g. using reports) Clicker questions (readiness + appropriateness for intervention) [pre-intervention only]
2	Measured at multiple time points (periodically) only in post-intervention period for all or selected subjects (patients or providers)	% of patients eligible to use eSyM completing 1+ qnr (PRIMARY IMPLEMENTATION OUTCOME) # pts assigned to eSyM/total # of pts with index condition on eSyM registry # reporting eSyM once, 25%, 50%, 75% of prompts Clinical staff responses to eSyM reports (InBasket + Telephone Encounters + Messages) Patient eSyM Total Usage Rate (w/MyChart) - up to 1 year after go-live Patient eSyM Total Usage Rate (w/ or w/o MyChart) - up to 1 year after go-live Patient eSyM Weekly Usage Rate (w/MyChart) - up to 1 year after go-live Patient eSyM Weekly Usage Rate (w/ or w/o MyChart) - up to 1 year after go-live % of MyChart Patients w/ documented outreach - up to 1 year after go-live % of patients with eSyM assigned w/ documented outreach - up to 1 year after go-live % of weekly patients responding to eSyM w/ documented outreach - up to 1 year after go-live % of weekly responders reporting moderate-severe symptoms - up to 1 year after go-live % of weekly responders reporting severe symptoms - up to 1 year after go-live

3	Measured from selected subjects (patients or providers) at a single time point, which could be during the pre-intervention period or the post-intervention period. For some subjects, data may be collected at both periods.	program barriers (stakeholder survey)
		Program facilitators (stakeholder survey)
4	Measured periodically through the SW-CRT design from all eligible subjects.	# of telephone encounter per patient per month

Notes:

- Both patient adoption and clinician utilization can be observed from analyzing EHR data based on eSyM utilization patterns. Clinician utilization can also be measured from the EHR and will be grouped in categories.
- Data for Aim 3a (clinicians) will be collected from the EHR based on system utilization patterns as well as from qualitative and quantitative survey, especially interviews with participating staff and clinicians.
- Appropriateness and acceptability will be ascertained using Weiner's AIM surveys (8-items total) which will be administered along with CAHPS surveys. Appropriateness and acceptability ratings will be defined based on the % of respondents who "agree" or "completely agree" with the survey items compared to the % who are neutral, disagree, or completely disagree and characterized using descriptive statistics.²³

8.2. Data Analysis

Analysis of Outcomes classified as Type 1: See Section 6.2

Analysis of Outcomes classified as Type 2: See Section 6.2

Analysis of Outcomes classified as Type 3: See Section 6.2

Analysis of Outcomes classified as Type 4: See Section 6.2

9. Analysis for Aim 3b: The sustainability of ePRO symptom management within a health system

Hypotheses:

- (1) We hypothesize that 3 or more of our health systems will continue eSyM reporting for MO patients beyond 90 days.
- (2) We hypothesize that tapering the dedicated nursing support provided by the study does not affect the effect of eSyM on clinical/utilization outcomes.

Analysis:

We will evaluate sustainability at the patient, clinic and health system level using simple rates and proportions. To evaluate sustainability, we will examine the consequences of withdrawing grant-funded nursing support for symptom management in the post-implementation period. We will compare outcomes from Period 6 (study month 45-50, all sites eSyM+) and the post-Implementation (Post-I; study months 51-56). Sites are trained and empowered to manage eSyM autonomously without research study staff. Then, during post-implementation, dedicated nursing support to monitor eSyM is *tapered* in half the sites (see Figure C2). To examine whether backing off on the study support attenuates the effect, we will perform difference in difference analysis. For each outcome, we will calculate the difference between Post-I and Period 6 outcomes by site. We then calculate the difference between site groups and the corresponding 95% confidence intervals.

10. Analysis for Aim 3c (Penetration and scalability of ePROs for symptom management) and Aim 3d (Extent of adaptation of ePRO systems over the course of the implementation process)

A mixed-methods approach:

Our analytic approach will integrate qualitative and quantitative data to obtain an informative description of factors that influence implementation at the level of 1) the practice site, 2) the health system, and 3) the entire project. The CFIR schema will facilitate comparisons, across settings and timepoints. First, we will analyze the qualitative and quantitative data separately. Next, we will use a weaving approach to integrate each source narrative to report findings on a theme-by-theme basis.²⁴

Qualitative:

Analysis of interviews and group discussions will rely on notes and transcribed audiotapes entered in NVivo software. Given the study purpose, we will use a framework analysis²⁵⁻²⁷ approach that allows for systematic analysis that is also flexible and iterative in nature.²⁸ Through indexing, charting, and mapping we will be able to draw comparisons across interviews to identify facilitators and barriers. Lastly, we will use the CFIR qualitative data scoring schema (**Table 14**) to assign a numeric code ranging from -2 to +2 to each construct summarizing whether it was a negative or positive influence on eSyM use. The weighted kappa statistic, with 0.70 as the cut-off will be used to assess agreement between coders. Ratings will be used to make topographic maps to visually convey the relative importance of each CFIR construct.²⁹

Table 14: Rating the Influence of CFIR Constructs on Implementation Outcomes	
-2	Negative influence, impeding influence in implementation efforts
-1	Negative influence, impeding influence in implementation efforts (general impression but no concrete examples given during interviews; mixed effect)
0	Neutral influence; contradictory interviews
+1	Positive influence, facilitating influence in implementation efforts (general statements but no concrete examples; mixed effect, but generally positive)
+2	Positive influence, facilitating influence (firm examples shown or given)
missing	Lack of interviewee input or absence of evaluable construct

Quantitative:

Clinician surveys will use ordinal response scales to capture the valence (+/- influence) for each CFIR construct and simple descriptive statistics to characterize responses. Finally, variables organized by CFIR domain will be combined with qualitative data on a theme-by-theme basis. This will provide an interpretable numeric summary of the perceived importance of each construct. We will use 95%

confidence intervals as a measure of precision. All analyses at the health system level will adjust for clustering using generalized linear mixed effects models.

11. References

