3.1. Randomization

This SW-RCT has 6 steps (figure below), and we randomize 6 sites (**Table 2**) to each of these steps. To ensure that two sites with the same region were not assigned to the same rollout step group (medical oncology live before surgery or surgery live before medical oncology), we employed a stratified randomization by region. As a result, each of the two groups has a site from each of the three regions (Northern, Southern, and Metropolitan). The stepped wedge design includes seven time-periods, including a run-in period (Figure).

Figure: SIMPRO Stepped-Wedge Randomization Schema

Abbreviations: BAPT=Baptist, WVU=West Virginia University, MMC=Maine Medical Center, DHMC=Dartmouth Hitchcock Medical Center, LCI=Lifespan Cancer Institute, DFCI=Dana-Farber Cancer Institute, SIMPRO=Symptom Management Implementation of Patient Reported Outcomes in Oncology

Sequence	Group	Site	eSyM version	Period 1	Period 2	Period 3	Period 4	Period 5	Period 6	Period 7
				Mar '19 - Aug '19	Sep '19 - Feb '20	Mar '20 - Aug '20	Sep '20 - Feb '21	Mar '21 - Aug '21	Sep '21 - Feb '22	Mar '22 - Aug '22
Med Onc live Before Surgery	Southern	BAPT	Med	Pre-live	Live					
			Surg	Pre-live						Live
	Northern	MMC	Med	Pre-live		Live				
			Surg	Pre-live					Live	
	Metrop-olitan	DFCI	Med	Pre-live			Live			
			Surg	Pre-live				Live		
Surgery live Before Med Onc	Metrop-olitan	LCI	Med	Pre-live				Live		
			Surg	Pre-live			Live			
	Northern	DHMC	Med	Pre-live				Live		
			Surg	Pre-live		Live				
	Southern	WVU	Med	Pre-live					Live	
			Surg	Pre-live	Live					

Note: The timing of medical and surgical rollouts is not the same at each site in this SW-RCT. The timing of medical and surgical rollouts was determined so that the number of subjects on the intervention and control would be the same in each site, when medical and surgical cohorts were combined.

Table 2: Six participating sites and Region

Site	Region
WVU	Southern
BAPT	
DHMC	Northern
MMC	
DFCI	Metropolitan
LCI	

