3.3. Number of Subjects

Considering the 2016 tumor registry-reported analytic case volume at each study site for thoracic, GI and Gyn cancers, 12 patients per month per site for each of surgical and medical oncology is a highly conservative estimate of accrual. With 6 sites, assuming equal cluster size, 432 patients will be enrolled both for each period and for each cohort. Thus, a minimum of 6048 patients are expected to be enrolled to the SW-CRT. (Table 3) We will not have a cap for the number of participants for each site. Thus, the number of participants at the end of the study will be different from site to site.

Table 3: Conservative estimates of the accrual numbers for the SW-CRT

Site	MO/ Surg	Period 1 (Run-in)	Period 2	Period 3	Period 4	Period 5	Period 6	Period 7	Total
BAPT	MO	72	72	72	72	72	72	72	504
	Surg	72	72	72	72	72	72	72	504
MMC	MO	72	72	72	72	72	72	72	504
	Surg	72	72	72	72	72	72	72	504
DFCI	MO	72	72	72	72	72	72	72	504
	Surg	72	72	72	72	72	72	72	504
LCI	MO	72	72	72	72	72	72	72	504
	Surg	72	72	72	72	72	72	72	504
DHMC	MO	72	72	72	72	72	72	72	504
	Surg	72	72	72	72	72	72	72	504
WVU	MO	72	72	72	72	72	72	72	504
	Surg	72	72	72	72	72	72	72	504
Total	MO	432	432	432	432	432	432	432	6048
	Surg	432	432	432	432	432	432	432	

Notes:

- The length of each period is 6 months. The run-in period will be at least 6 months, and it will be adjusted so that the total number of eligible episodes under the control condition can be identical to that under the intervention condition.
- The cells colored by blue or grey indicate the periods where the intervention is rolled out in that hospital.

A subset of eSyM+ patients will be asked to complete a research questionnaire called the “SASS Questionnaire (eSyM+ version)” asking about their Self-efficacy, Attainment of information needs, Symptom burden, and Satisfaction with care.

Table 4: SASS Questionnaire accrual numbers (Survey Cohort)							
Site	Surgery			Medical Oncology			Totals
	eSyM- Version	eSyM+ Version	eSyM+ Non-Responder Version	eSyM- Version	eSyM+ Version	eSyM+ Non-Responder Version	
Site 1	75	75	15	75	75	15	330
Site 2	75	75	15	75	75	15	330
Site 3	75	75	15	75	75	15	330
Site 4	75	75	15	75	75	15	330
Site 5	75	75	15	75	75	15	330
Site 6	75	75	15	75	75	15	330
Totals	450	450	90	450	450	90	1,980

eSyM+ : Intervention condition
eSyM- : Control condition

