4.7. Power Considerations

We estimate a minimum of 6048 patients will be enrolled. (see Section 3.3 for details). Since some subjects may experience more than one trigger event (see Section 4.2 General Analysis Approach: *Multiple episodes for medical record data*), the study participants will potentially contribute multiple data points. The goal of the power calculation for this study is to confirm that the study has sufficient power to assess the effects of the intervention on the outcomes. Therefore, for the power calculations throughout this SAP, we will conservatively estimate the power, assuming that an individual patient provides only one episode.

The probability that a patient who has a trigger event experiences EDTR within 30 days after the trigger event is estimated to vary between 8% to 15% for the control group, based on the HCUP data, institutional data, and early phase analyses from CMMI's Oncology Care Model for Baptist Memorial, the only Oncology Care Model participant among our 6 sites. We hypothesize that the probability of experiencing EDTR by Day 30 will be 3 to 4% lower in the eSyM+ group.

Table 9 shows the required sample sizes for the study to have 80% power to detect the difference between groups, at two-sided alpha level 0.05, using the SW-RCT design.¹⁴ Analyses of inter-institutional variation in hospitalization rates and ED visit rates from AHRQ's statewide databases indicate that low ICC estimates are appropriate.^{15,16} Furthermore, we expect a low ICC because: 1) the intervention will be deployed using the same technology across sites; 2) we will adjust for variation in baseline risk via GLMMs such that any potential differences in case-mix among sites will be negligible. Given these factors, the conservative estimate of 6048 participants provides adequate power to address the Aim 2a primary outcome.

Note that we used the sample size formula¹⁴ that assumes exchangeable correlations because we originally had planned to include sites as random effects. However, since the number of sites is only 6 in this study, we modified the analysis plan and decided to include sites as fixed effects in the primary analysis. We acknowledge that our original sample size calculation (above) may not be precise due to this, but it should still work as a conservative estimate.

Table 9. Required total sample size with various scenarios for 80% power					
The probability of experiencing EDTR by Day 30		Effect size		N required	

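### SAP section 9 hypothesises that tapering nurse support leaves eSyM's effect unchanged, but its three-against-three-site comparison has no margin or decision rule, so an interval covering zero could be taken as support

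*SAP*

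**What the plan says.** Aim 3b (SAP section 9) states two hypotheses. The first has a numeric criterion: at least three health systems continue eSyM reporting for medical oncology patients beyond 90 days. The second has none: "We hypothesize that tapering the dedicated nursing support provided by the study does not affect the effect of eSyM on clinical/utilization outcomes".

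The comparison for the second is set out as: "We will compare outcomes from Period 6 (study month 45-50, all sites eSyM+) and the post-Implementation (Post-I; study months 51-56". In the later period, dedicated nurse support is tapered in half of the sites. To see whether this weakens the effect, "we will perform difference in difference analysis": the change between the two periods is computed for each site and outcome, and then "We then calculate the difference between site groups and the corresponding 95% confidence intervals".

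Section 9 does not single out an outcome. It gives no equivalence or non-inferiority margin, no power or precision figure, and no rule for when hypothesis (2) counts as supported. Other parts of the SAP are more careful. Section 4.5 concedes insufficient power for EDTR in subgroups and calls those analyses exploratory. Section 5.3 gives detectable differences for Aim 2b.

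The size of the effect that tapering might erode is in SAP section 4.7: "We hypothesize that the probability of experiencing EDTR by Day 30 will be 3 to 4% lower in the eSyM+ group".

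**The concern.** Hypothesis (2) claims the absence of an effect. An ordinary 95% interval can count against such a claim by excluding zero. It can count in favour only if it is narrow enough to rule out a loss that matters, and that requires a stated size of loss. Section 9 gives none. An interval that covers zero is then easily taken as support, whether it covers zero because tapering is harmless or because six sites cannot tell.

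Whether eSyM keeps working without grant-funded nurses is a main implementation conclusion. If the interval is wide compared with the whole eSyM benefit, the report could describe tapering as harmless when the data are compatible with complete loss of that benefit.

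**Working it through.** The SAP gives no Aim 3b figure to reproduce, so the check is of the precision that the design can deliver. EDTR by Day 30 is used as an example, because it is the outcome with a planned effect size.

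**Inputs**
- Sites: "we randomize 6 sites" (SAP 3.1). Half are tapered, so 3 v 3.
- Minimum accrual: "12 patients per month per site for each of surgical and medical oncology is a highly conservative estimate of accrual" (SAP 3.3). Over a 6-month period this is 12 × 6 = 72 per cohort, so m = 144 per site-period for both cohorts. The same inputs reproduce the SAP total: 72 × 6 sites × 2 cohorts × 7 periods = 6,048.
- EDTR rate: section 9 describes all sites as eSyM+, so p is taken from the intervention column of Table 9, 5% to 11%, with 8% as a central value.
- Benefit at stake: 3 to 4 points (SAP 4.7).

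**Standard error.** One site's change has variance 2p(1−p)/m. The difference between two means of three sites has variance (2/3) × 2p(1−p)/m, so SE = √[4p(1−p)/(3m)]. At p = 8% and m = 144: √[4 × 0.08 × 0.92/432] = 2.61 points.

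**95% half-width.** Multiply by 1.96 (patient-level, normal), or by 2.776 (t with 4 df, from six site changes in two groups).

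| Patients per site-period | p | SE | Half-width, normal | Half-width, t |
|---|---|---|---|---|
| 144 (planned minimum) | 5% | 2.10 | 4.1 | 5.8 |
| 144 | 8% | 2.61 | 5.1 | 7.2 |
| 144 | 11% | 3.01 | 5.9 | 8.4 |
| 271 (13,000/48) | 8% | 1.90 | 3.7 | 5.3 |
| 625 (30,000/48) | 8% | 1.25 | 2.5 | 3.5 |

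The last two rows assume an even spread over 6 sites and the 8 periods of SAP 3.6 (48 site-periods). The 13,000 is the patient count in protocol Activity 5. The 30,000 is the study-wide ceiling over all activities in protocol section 6, so that row is optimistic.

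**Chance of detecting complete loss of the benefit, p = 8%**
- Minimum accrual: 21% (3 points) to 33% (4 points) with the normal, 15% to 22% with t.
- 13,000 patients: 35% to 56%, or 23% to 36%.
- 30,000 patients: 67% to 89%, or 45% to 67%.

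At minimum accrual and p = 8%, the loss detectable with 80% power is 7.3 points (normal) or 9.8 (t), roughly two to three times the whole benefit.

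**Site-by-period variation.** The figures above ignore it. With m = 144, p = 8%, the Table 9 ICCs and an assumed cluster autocorrelation of 0.8, the half-width becomes 5.8 (normal) or 8.2 (t) at ICC 0.01, and 7.9 or 11.2 at ICC 0.05.

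**What a margin would require.** With no true loss, 80% power and one-sided 0.025 (normal), patients per site-period = (1/3) × 4p(1−p) × [(1.96 + 0.842)/margin]². A 3-point margin at p = 8% needs 856 (553 at 5%, 1,139 at 11%). A 4-point margin at 8% would need 482. The planned minimum is 144.

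**The case against.** The strongest reply is that section 9 plans estimation, not a test. It states no p-value and no reading rule, its declared purpose is to look for attenuation, and a reader can set the interval beside the planned 3 to 4 points and see that it is wide. This largely stands. A reader might infer that any result short of a huge loss would be declared confirmation, but the SAP does not say so. The text supports only that a null-looking interval could be used that way, because nothing prevents it.

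A second reply is that accrual has no cap and the 12 per month is called conservative. This also stands in part. It would be wrong to infer that the interval covers zero whatever tapering does: a large enough loss would show even at the minimum, and precision improves with numbers. But at 13,000 patients the half-width at 8% is still about as large as the benefit or larger. Only near the ceiling does the normal half-width fall below 3 points, and the t half-width stays above 3.

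Third, section 9 does not fix sites as the unit of inference, and the Aim 2a primary model treats sites as fixed effects. The t figures are therefore one reading; the normal figures are the favourable one. EDTR is also only an example, and other outcomes may differ.

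Fourth, part of the sustainability evidence is sound already: hypothesis (1) has a numeric criterion and Table 13 lists process measures. None of these replies supplies the missing margin or rule for hypothesis (2).

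**Conclusion.** The point holds as a gap between hypothesis and analysis. Hypothesis (2) asserts no effect, and the planned comparison offers no way to support it other than failing to find a difference. For EDTR at the planned minimum, the 95% half-width is 4.1 to 5.9 points (normal) or 5.8 to 8.4 (t), against a total planned benefit of 3 to 4 points. An interval covering zero would then be the more likely result even if tapering removed the whole planned benefit.

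This rests on EDTR as the example outcome, eSyM+ rates from Table 9, equal site sizes and no site-by-period variation, which would widen the interval. It also takes 3 v 3 from the SAP's words, since the figure cited for the tapering design was not available to me. The documents do not show that the investigators intend to claim confirmation from a null result. This is a secondary implementation question and does not touch the primary endpoint.

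**What to change.** Change the wording of SAP section 9 in one of two ways.

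(a) Name one outcome and a fixed margin set in advance, no larger than the 3-point planned effect in section 4.7. Claim that the effect is sustained only if the upper 95% limit for the increase under tapering lies below that margin; otherwise report the result as inconclusive. The margin should not be derived from the Aim 2a estimate, which depends on the data and gives no usable margin if Aim 2a shows no benefit.

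(b) Label hypothesis (2) descriptive, report the interval beside the planned 3 to 4 points, and make no claim of no effect.

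In either case, state the expected precision at the accrual achieved, and rest the sustainability conclusion on hypothesis (1) and the process measures already in Table 13, such as usage and documented outreach. Given the sizes above, (b) is the more realistic choice for EDTR.

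In the same edit, reconcile the baseline period. Section 9 treats Period 6 as fully eSyM+, but in SAP section 3.6 Period 6 ends in February 2022, while BAPT surgery and WVU medical oncology went live in April 2022.

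No new data are needed. The cost is a less favourable conclusion, likely to be inconclusive for EDTR.

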3.6. Extension of accrual period

Due to COVID, the number of observed ER events was smaller than the expected number in three SIMPRO sites as of April 2022. The study team decided to extend accrual an extra 6 months (1 additional study period) to allow for additional event collection and patient recruitment. The extension will also allow sites who recently went live to continue program optimization and stabilization. The figure (below) depicts the revised study design with Period 8.

Statistical Analysis Plan for Protocol Activity 4: Pragmatic Stepped-Wedge Cluster Randomized Trial
SIMPRO Research Center: Integration and Implementation of PROs for Symptom Management in Oncology Practice

Sequence	Group	Site	eSym version	Period 1	Period 2	Period 3	Period 4	Period 5	Period 6	Period 7	Period 8
				Mar '19 - Aug '19	Sep '19 - Feb '20	Mar '20 - Aug '20	Sep '20 - Feb '21	Mar '21 - Aug '21	Sep '21 - Feb '22	Mar '22 - Aug '22	Sept '22 - Feb '23
Med Onc live Before Surgery	Southern	BAPT	Med	Pre-live	Go-Live – 9/10/2019						
			Surg	Pre-live							Go-Live – 4/25/2022
	Northern	MMC	Med	Pre-live	Go-Live – 3/16/2020						Go-Live – 10/19/2021
			Surg	Pre-live							
	Metropolitan	DFCI	Med	Pre-live	Go-Live – 9/22/2020 (2 clinics), 11/17/2020 (1 clinic)						
			Surg	Pre-live	Go-Live – 5/4/2021 (1 clinic), 6/15/2021 (2 clinics), 10/12/2021 (1 clinic)						
Surgery live Before Med Onc	Metropolitan	LCI	Med	Pre-live							Go-Live – 9/21/2021
			Surg	Pre-live	Go-Live – 11/24/2020						
	Northern	DHMC	Med	Pre-live							Go-Live – 11/30/2021
			Surg	Pre-live	Go-Live – 4/28/2020						
	Southern	WVU	Med	Pre-live							Go-Live – 4/18/2022
			Surg	Pre-live	Go-Live – 10/25/2019						

4. Analysis for Aim 2a: Healthcare utilization, measured by the need for emergency and acute care

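### The Aim 3b sustainability baseline in SAP section 9 matches neither the SAP's own period numbering nor the Period 8 extension, and study month 1 is not defined

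*SAP*

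**What the plan says.** SAP section 9 plans a difference-in-differences for Aim 3b.

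- **Baseline:** "We will compare outcomes from Period 6 (study month 45-50, all sites eSyM"+).
- **Comparison window:** "and the post-Implementation (Post-I; study months 51-56"), the six months directly after the baseline.
- **Exposure:** in that second window, "dedicated nursing support to monitor eSyM is *tapered* in half the sites".
- **Estimator:** "For each outcome, we will calculate the difference between Post-I and Period 6 outcomes by site". The site changes are then contrasted between the two groups of sites, with a 95% interval.
- **Hypothesis (2):** tapering "does not affect the effect of eSyM on clinical/utilization outcomes".

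The calendar is set elsewhere. SAP Table 3 labels its first column "Period 1 (Run-in"), and its notes say "The length of each period is 6 months". The SAP schedule runs in six-month blocks from March 2019. The randomization part of protocol section 10.0 has seven periods too, but labels them run-in plus Periods 1 to 6. SAP section 3.6 reports the actual go-live dates and the extension: "The study team decided to extend accrual an extra 6 months (1 additional study period"), which is Period 8, September 2022 to February 2023. Section 9 does not mention Period 8, and the June 2024 addendum leaves section 9 unchanged.

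**The concern.** A taper contrast needs a baseline in which the contributing cohorts already have eSyM with full support. If part of a site's baseline is pre-live, that site's change into Post-I contains the first effect of eSyM as well as any effect of reduced nursing support.

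The direction of error depends on which sites taper. If the late-switching sites taper, the arriving benefit of eSyM hides a loss of effect. If they keep their support, tapering looks more harmful than it is.

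There is also a possible link to the effectiveness analysis. If the taper window lies inside trial accrual, reduced-support episodes enter the eSyM+ condition. SAP Table 8 has no variable for taper and section 4.6 has no sensitivity analysis for it.

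**Working it through.** **Inputs.** Period dates and go-live dates come from SAP section 3.6. Table 3 gives 72 patients per cohort, site and period, so both cohorts of a site weigh equally. SAP section 4.7 gives the hypothesised effect of 3 to 4 points. As a check on the grid, 12 site-cohorts × 7 periods × 72 = 6,048, which is the SAP's total. DFCI surgery is counted live from its first clinic, although one clinic went live on 12 October 2021, so pre-live time is slightly understated.

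**The two readings of Period 6**

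| | SAP numbering | Protocol numbering |
|---|---|---|
| Baseline | Sep 2021 – Feb 2022 (SAP Period 6, 181 days) | Mar – Aug 2022 (SAP Period 7, 184 days) |
| Post-I | Mar – Aug 2022 (SAP Period 7) | Sep 2022 – Feb 2023 (SAP Period 8) |
| Implied study month 1 | Jan 2018 | Jul 2018 |

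**Pre-live days in each window**

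| Site-cohort | Go-live | SAP Period 6 | SAP Period 7 |
|---|---|---|---|
| BAPT surgery | 25 Apr 2022 | 181 of 181 | 55 of 184 |
| WVU medical oncology | 18 Apr 2022 | 181 of 181 | 48 of 184 |
| DHMC medical oncology | 30 Nov 2021 | 90 of 181 | 0 |
| MMC surgery | 19 Oct 2021 | 48 of 181 | 0 |
| LCI medical oncology | 21 Sep 2021 | 20 of 181 | 0 |
| Other seven | before Sep 2021 | 0 | 0 |

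Pre-live share of site-cohort time:

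- SAP Period 6: (181 + 181 + 90 + 48 + 20) / (12 × 181) = 520 / 2,172 = 23.9%.
- SAP Period 7: (55 + 48) / (12 × 184) = 103 / 2,208 = 4.7%.
- SAP Period 8: 0. It is the first period with every site-cohort live from day 1.

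In SAP Period 6 the two all-control cohorts hold 2 × 72 = 144 of 12 × 72 = 864 planned patients (16.7%). They are half of the planned baseline patients at BAPT and at WVU.

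**Shift in the taper contrast.** I assume even accrual within a period, three tapering sites against three others, and a constant eSyM effect of 3 to 4 points. The shift is that effect times the difference between groups in the mean rise in live share. A site's live share is the mean over its two cohorts.

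*SAP numbering (Period 6 to Period 7).* Rise in live share:

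- BAPT: 0.500 − (55/184)/2 = 0.351
- WVU: 0.500 − (48/184)/2 = 0.370
- DHMC: (90/181)/2 = 0.249
- MMC: (48/181)/2 = 0.133
- LCI: (20/181)/2 = 0.055
- DFCI: 0

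The worst split sets BAPT, WVU and DHMC against MMC, LCI and DFCI: (0.351 + 0.370 + 0.249)/3 − (0.133 + 0.055 + 0)/3 = 0.26. Times 3 to 4 points, this is 0.8 to 1.0 point. A balanced split, such as BAPT, DHMC and DFCI against the rest, gives 0.014, or about 0.04 to 0.06 point.

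*Protocol numbering (Period 7 to Period 8).* Only BAPT (0.149) and WVU (0.130) change. With both in one group: (0.149 + 0.130)/3 = 0.093, or 0.3 to 0.4 point.

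**Other origins for study month 1**

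- November 2018 (randomization): Post-I is January to June 2023, which shares two months with Period 8.
- March 2019 (start of Period 1): Post-I is May to October 2023, outside Period 8.

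Both windows, and both in the first table, end before 31 March 2024, when the protocol's eSyM+ cohort closes (section 5.0, Activity 4).

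**Precision for hypothesis (2).** With 144 patients per site and period and binomial variation only, the standard error of the contrast is √[(2/3) × 2p(1 − p)/144]. At p = 8%, 10% and 15% this is 2.6, 2.9 and 3.4 points. The 95% half-width is 7.2, 8.0 and 9.5 points with t on 4 degrees of freedom, or 5.1 to 6.7 points over the same range with a normal interval. All exceed the whole hypothesised effect.

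**The case against.** The best defence is that section 9 carries the protocol's period numbers. Period 6 then means SAP Period 7, every cohort was scheduled to be live, and the claim of full exposure fails only by a go-live lag of 7 to 8 weeks in two cohorts. The likely fault is a stale label. This is plausible, but the SAP numbers periods differently everywhere else, and an analyst following it would use the wrong six months.

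A second defence counts sites rather than site-cohorts: every site had at least one cohort live by 24 November 2020. That rescues the phrase but not the estimator, which is computed by site with no restriction to live cohorts.

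Stronger readings are tempting, and the documents do not support them:

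- A reader might infer that the baseline holds two all-control cohorts and also that the taper falls on Period 8. Post-I directly follows the baseline, so the first needs the SAP's numbering and the second the protocol's. They cannot both hold.
- A reader might infer that the primary analysis is contaminated by tapered support. Both numberings place Post-I on trial accrual, but the actual taper dates cannot be checked. The SAP points to a Figure C2 that is not in the available text, and its absence here is not a fault of the plan. The primary comparison is pragmatic and by exposure. Section 4.4 also has a sensitivity analysis of effect by time since rollout, though this does not isolate taper.
- A reader might infer that hypothesis (2) requires a non-inferiority margin. Section 9 plans an estimate with an interval and nowhere says that an interval containing zero proves the hypothesis. The half-widths above are also only one construction: the SAP gives no interval method and calls its accrual figure highly conservative, and the protocol reports more than 13,000 patients. Larger numbers would narrow them.

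**Conclusion.** The concern holds as a failure of alignment. Section 9 fits neither the SAP's period numbering nor the Period 8 extension, and study month 1 is undefined, so the two windows cannot be identified.

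- **In the SAP's calendar**, the statement that all sites are eSyM+ at baseline is wrong at cohort level. The possible shift runs from near zero to about 1.0 point, and Post-I is Period 7, when the last two cohorts first go live.
- **In the protocol's numbering**, the baseline is sound apart from a short lag (at most 0.3 to 0.4 point), and the open question is the coincidence of Post-I with Period 8.

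These sizes rest on equal cohort weights, even accrual, a three-against-three taper and a constant 3 to 4 point effect. They are small beside the likely interval, but they are avoidable bias in a contrast meant to detect loss of that same effect. The point affects secondary Aim 3b. It reaches the primary EDTR analysis only if the taper overlapped accrual.

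**What to change.** In SAP section 9:

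1. Define study month 1 and give calendar dates for the baseline and Post-I windows, using the SAP's period numbers.
2. Restrict the baseline to time when the contributing site-cohorts are live. All 12 are live from 25 April 2022.
3. State which sites tapered and when. If that window overlaps trial accrual, flag the tapered site-episodes and repeat the Aim 2a analysis without them as a sensitivity analysis.
4. Report the hypothesis (2) contrast with its interval, and say that an interval containing zero will not be read as proof of no effect.

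The cost is a few lines of SAP text, a shorter baseline window with some loss of precision, and one extra sensitivity run if the overlap is confirmed.
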